8.1 Interim Analysis

Bioequivalence for AUC:

A mixed model will be applied to log-transformed AUC0-t and AUC0-∞ with treatment, period and sequence as fixed effects, and subject (sequence) as a random effect. Based on the residual error term 90% confidence intervals will be computed for the estimated differences Test − Reference, resulting in 90% confidence intervals for the Test/Reference ratios after backtransformation.

Bioequivalence for Cmax:

The 90% confidence intervals will be computed for the estimated differences Test – Reference. If $CV_{WR} \leq 30$ the procedure to estimate is the same as the confidence intervals for AUC, if $30\% < CV_{WR} \leq 50\%$, the acceptance interval will be widened according to the next formula (U, L) = $\exp(\pm k'sWR)$, where U is the upper limit, L is the lower limit, k is the constant established as 0.760 and sWR is the intrasubject standard deviation for the Cmax log transformated value for reference product. For values greater than 50% the aceptace range going to be 69.84 – 143.19

TO evaluate the group effect, the next codes will be used: PROC GLM DATA=PK

CLASS SEQ SUBJ PER TRT GROUP;

MODEL LNPARAM=SEQ PER TRT GROUP GROUP*TRT SUBJ(TRT)/ DDFM=SATTERTH;

LSMEANS TRT/ ADJUST=T PDIFF CL ALPHA=0.10.

TEST H=SEQ E=SUBJ(TRT);

RUN;

QUIT;

Statistical analysis for secondary parameters

The secondary pharmacokinetics parameters (Tmax, AUCextrapolated, t½, Cl/F and Vd/F) going to be analyzed by descriptive statistics

9 Changes to the Planned Analyses in the Clinical Trial Protocol

The statistical methods as described in the protocol were adopted.

There are no changes to the planned analyses.

10 Protocol Deviations and Analysis Sets

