5.1 Overall Trial Design and Plan

The purpose of the current relative bioavailability trial is to assess the bioequivalence (BE) of the the new 600 mg Cisticid tablet (Test) versus Biltricide (Reference) in healthy male volunteers under fed conditions.

This is a phase I, crossover, open-label, single dose, randomized, three period trial where subjects will be randomized to one of three sequences: T-R-R, R-T-R and R-R-T where T is test product and R is Reference product, with a washout period of at least 1 week in between.

The study will investigate the BE of the new 600 mg Cisticid tablet versus the comparator 600 mg tablet of Biltricide at a dose of 1200 mg (primary endpoints AUC_{0-t} and C_{max} of L-PZQ), administered in fed condition in 60 healthy male volunteers. Finally safety and tolerability will be also investigated.

In each treatment period subjects are institutionalized the evening before dosing until 24 hours after dosing with a washout period of 7 days. Total duration of the study for a subject is up to 7 weeks, including a Screening period of maximal 28 days, and 3 weeks dosing period including washout, and safety follow-up (EoT visit) at 7 days after third dose (period).

The subjects will be randomized to one of the 3 treatment sequences (see [Table 2](#) below).

Table 2 Treatment Sequences of the Study.

| Sequence | Period 1 | | Period 2 | | Period 3 | |
|----------|-----------|-----------------|-----------|-----------------|-----------|-------------------------------|
| 1 | Test | Wash-out 7 days | Reference | Wash-out 7 days | Reference | Wash-out 7 days and EOT visit |
| 2 | Reference | | Test | | Reference | |
| 3 | Reference | | Reference | | Test | |

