6.2 Dosage and Administration

Single dose, oral administration of 1200 mg Praziquantel (two 600 mg tablets) with 250 ml water, in each period, after the breakfast. A mouth check will be performed after each administration. The subject will take investigational medical product between 08:00 till 08:09 h, in 4 groups of 5 subjects each, with a 3-minute gap among each group for dosing

Subjects will enter the clinic the day before dosing (in 3 groups of 20 participants) and must fast overnight before IMP administration.

Dosing in the non-fasted state should be done at 30 minutes after the start of a standardized normal breakfast. The breakfast should be eaten within a period of 20 minutes and time should be recorded. Compliance with breakfast consumption will be recorded. All subjects will fast for 5 hours after dosing/completion of breakfast. At 5 hours after dosing, subjects will receive a light lunch.

The start of dosing between the three groups listed below will be separated by approximately three days, e.g. Group 2 dosing will start approximately three days after Group 1 has started.

During each period one of the three treatments will be dosed from 08:00 till 08:09 h, in 4 groups of 5 subjects each, with a 3-minute gap among each group for dosing. Group's distribution and timing can be changed due to operational reasons, as long as there is no impact in the study results.

Group's distribution, subjects and dose schedules are shown in the [Table 4](#):

Table 4 Dosing Scheme

| | Subgroups | No. of subjects | Dosing schedule |
|---------|-----------|------------------------|-----------------|
| Group 1 | A | 01, 02, 03, 04 and 05 | 08:00 h |
| | B | 06, 07, 08, 09 and 10 | 08:03 h |
| | C | 11, 12, 13, 14 and 15 | 08:06 h |
| | D | 16, 17, 18, 19 and 20 | 08:09 h |
| Group 2 | E | 21, 22, 23, 24, and 25 | 08:00 h |
| | F | 26, 27, 28, 29, and 30 | 08:03 h |
| | G | 31, 32, 33, 34, and 35 | 08:06 h |
| | H | 36, 37, 38, 39, and 40 | 08:09 h |

| | Subgroups | No. of subjects | Dosing schedule |
|---------|-----------|-----------------------|-----------------|
| Group 3 | I | 41, 42, 43, 44 and 45 | 08:00 h |
| | J | 46, 47, 48, 49 and 50 | 08:03 h |
| | K | 51, 52, 53, 54 and 55 | 08:06 h |
| | L | 56, 57, 58, 59 and 60 | 08:09 h |

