8.2 Randomization

Valid statistical inferences are generally derived by assuming that errors in the observations are distributed independently, in random variables. Randomization generally ensures validity of this hypothesis. Full randomization of subjects to the treatment's sequence will be made according to the design sequences based on the internal procedures from the PPD [REDACTED] compliant with the PPD [REDACTED] (28) using the PPD [REDACTED].

A total of 60 subjects are to be enrolled in the trial and randomized to one of 3 treatment sequences, such that 20 subjects are assigned to each treatment sequence.

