8.4.2 Analysis of Primary Endpoints

The analysis of the primary endpoints AUC_{0-t} and C_{max} of L-PZQ will be performed using the PK population. For the demonstration of bioequivalence different approaches will be applied for AUC_{0-t} and C_{max} . For AUC_{0-t} the standard approach will be followed, i.e. the point estimate and the 90% CI of the Test/Reference geometric mean ratio must fall within [0.80, 1.25]. AUC_{0-t} of L-PZQ will be log-transformed and analyzed using a generalized linear model as given by the SAS code below:

```
PROC GLM DATA=PK;
```

```
CLASS SEQ SUBJ PER TRT;
```

```
MODEL LNPARAM = SEQ PER TRT SUBJ(TRT) / DDFM=SATTERTH;
```

LSMEANS TRT / ADJUST=T PDIFF CL ALPHA=0.10.

TEST H=SEQ E=SUBJ(TRT);

RUN;

QUIT;

The treatment difference TEST – REFERENCE will be estimated, and the 90% CIs for the difference in LS-means will be calculated. The difference and 90% CIs will be back-transformed to the original scale. If the 90% CI for the ratio (test/reference) lies entirely within the interval [80.00 – 125.00], then the BE criterion is fulfilled for AUC_{0-t} .

For the analysis of C_{max} , a reference-scaled bioequivalence approach will be applied as follows:

Point estimate and 90% confidence interval will be computed as described above for AUC. If $CV_{WR} \leq 30\%$ for C_{max} (i.e. the within-subject CV for the reference drug is $\leq 30\%$), then the common acceptance range for bioequivalence will apply. For $30\% < CV_{WR} \leq 50\%$ the acceptance interval will be widened according to $[U, L] = \exp [\pm k \cdot sWR]$, where U is the upper limit of the acceptance range, L is the lower limit of the acceptance range, k is the regulatory constant set to 0.760 and sWR is the intrasubject standard deviation of the log-transformed values of C_{max} of the reference product. sWR will be calculated using the data under reference treatment only. For all values of CV_{WR} greater than 50% the acceptance range is fixed to [69.84 – 143.19].

The geometric mean ratio for C_{max} should always lie within [80.00 – 125.00].

- a. Descriptive statistics and boxplots will be provided by treatment.

CCI

PROC GLM DATA=PK;

CLASS SEQ SUBJ PER TRT GROUP;

MODEL LNPARAM = SEQ PER TRT GROUP GROUP*TRT SUBJ(TRT) / DDFM=SATTERTH;

LSMEANS TRT / ADJUST=T PDIFF CL ALPHA=0.10.

TEST H=SEQ E=SUBJ(TRT);

RUN;

QUIT;

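### The group-effect code gives the between-subject factor GROUP no between-subject error term, so it yields either no group test or one with an inflated false-positive rate (about 17-68% at nominal 5% if the intraclass correlation is 0.2-0.7)

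*SAP*

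**What the plan says.** Protocol 6.2 brings the subjects in as cohorts: "Subjects will enter the clinic the day before dosing (in 3 groups of 20 participants"). It adds that "The start of dosing between the three groups listed below will be separated by approximately three days". Table 4 assigns subjects 1-20, 21-40 and 41-60 to groups 1, 2 and 3, so each subject belongs to one group only.

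Protocol 5.1 sets the design: "subjects will be randomized to one of three sequences: T-R-R, R-T-R and R-R-T". Protocol 8.2 fixes the allocation, "such that 20 subjects are assigned to each treatment sequence".

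For the cohorts, SAP 8.1 says "TO evaluate the group effect, the next codes will be used" and gives a PROC GLM step with "MODEL LNPARAM=SEQ PER TRT GROUP GROUP*TRT SUBJ(TRT)/ DDFM=SATTERTH". Protocol 8.4.2 has the same model: "MODEL LNPARAM = SEQ PER TRT GROUP GROUP*TRT SUBJ(TRT) / DDFM=SATTERTH". The only statement that names an error term covers sequence: "TEST H=SEQ E=SUBJ(TRT"). There is no RANDOM statement and no TEST statement for GROUP.

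The SAP 8.1 text on AUC describes a mixed model with subject within sequence as random, but that model has no group term. Text directly before the protocol code is blacked out. No visible text gives a test level for the group analysis or says what follows from a significant result. Protocol 8.4.1 sets 0.05 as the general default.

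**The concern.** A factor that varies only between subjects has to be judged against variation between subjects. In this code GROUP falls to the default F test, whose denominator is the residual. With SUBJ(TRT) in the model, that residual contains only within-subject variation. The null hypothesis then tested is that there is no group effect and also no difference between subjects, and the second part is never true in practice.

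This is the only visible analysis of the three separately dosed cohorts. What is at stake is whether its group line can be believed. A reader could see no test at all, or could see a significant group effect that is only ordinary variation between subjects.

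**Working it through.** **Inputs.** 60 subjects, three periods, one test and two reference doses each (protocol 5.1); 20 per sequence (8.2); 3 groups of 20 (6.2); within-subject CV 39.5% for AUC and 52% for Cmax (8.1); nominal level 5% (8.4.1 default). The between-subject variance is not given. It enters below as r = s_b²/s_w², or as intraclass correlation ICC = r/(1+r).

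**The plan's own figure.** The documents state no error rate for the group test, so the nearest figure to reproduce is the sample size. With s_w² = ln(1+0.395²), standard error s_w·√(1.5/n), 2n−3 df, ratio 0.95 and limits 0.80-1.25, n = 48 gives 80.5% power, and 48/(1−0.20) = 60. Both agree with the plan.

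**Degrees of freedom, code as written.** There are 60 × 3 = 180 observations. SUBJ(TRT) spans 60 × 2 = 120 subject-by-treatment cells, and period adds 2, so the rank is 122 and the residual has 180 − 122 = 58 df. Each test dose has its own cell, so the residual comes only from the repeated reference doses: 60 differences less 2 for period. Every sequence, group and group-by-treatment contrast already lies within the 120 cells.

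- Adjusted for SUBJ(TRT): GROUP 0 df, GROUP*TRT 0 df.
- Taken in order: GROUP 2 df, GROUP*TRT 2 df, each against the 58-df residual.

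**Size of the sequential GROUP test.** With no group effect, the GROUP mean square expects s_w² + 3s_b² (three observations per subject) and the residual mean square expects s_w². The rejection rate is therefore P{F(2,58) > F_crit/(1+3r)}, with F_crit = 3.156.

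| ICC | r | 1+3r | F_crit/(1+3r) | Rejection, formula | Rejection, simulated |
|---|---|---|---|---|---|
| 0.2 | 0.25 | 1.75 | 1.803 | 17% | 17-18% |
| 0.3 | 0.43 | 2.29 | 1.381 | 26% | 25-26% |
| 0.5 | 1.00 | 4.00 | 0.789 | 46% | 46% |
| 0.7 | 2.33 | 8.00 | 0.394 | 68% | 67-68% |

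For AUC these ICCs correspond to a between-subject CV of √(exp(r·ln(1+0.395²))−1), about 19% to 63%. Outside that span the rate runs from 5% at r = 0 to 79% at r = 4. With the 59 subjects in the SAP tables, or with 48, the rates are nearly the same.

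The documents offer one indirect guide, the expected Cmax range of 38.0-566 ng/mL (protocol, Justification for Dose). With within-subject CV 52%, it implies r of about 0.4 if the source study had 60 subjects and 1.9 if it had 12. The rejection rate is then about 25% to 62%. The source size is not given.

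**GROUP*TRT in the same sequential table.** Simulated rejection under the null is about 5% at every ICC, assuming equal test and reference variances and no subject-by-formulation interaction.

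**Partial repairs.** Changing only SUBJ(TRT) to SUBJ(SEQ) makes GROUP*TRT testable (2 df), but GROUP still has 0 adjusted df and its sequential rejection is unchanged (18% to 68%). Adding only a TEST of GROUP against SUBJ(TRT) still gives 7-21% for r = 0.1 to 4, because that term mixes between- and within-subject variation.

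**Full repair.** With subject nested in sequence and group, and all nine sequence-by-group cells filled, the between-subject error has 60 − 9 = 51 df. The rank is 60 + 2 + 1 + 2 = 65 and the residual has 180 − 65 = 115 df. GROUP taken in order against the 51-df term rejects about 5% at every ICC, and GROUP*TRT against the residual also rejects about 5%.

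**The case against.** The strongest reply is that the defect sits in a supplementary main effect. A GROUP effect is a difference in exposure level between cohorts. Every subject receives both products, so that difference cancels within subject and does not bias Test/Reference. The term that bears on the ratio is GROUP*TRT, and its sequential test in this same code is sound. Its power for a 1.25-fold shift of the ratio in one group is about 31%, against about 32% under the corrected model (CV 39.5%). All of this stands.

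Two stronger readings are tempting, and the documents support neither. One is that a false group signal undermines the pooled ratio or the bioequivalence error rate. No visible rule connects the group result to that decision, and the blacked-out text before the protocol code may contain one, so nothing can be concluded either way. The other is that the interaction cannot be examined at all. That is true of the adjusted table only.

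It can also be said that the code would not run as typed, so the fault would be noticed. DDFM= belongs to PROC MIXED rather than PROC GLM, the LSMEANS line ends in a period, and the SAP lacks a semicolon after DATA=PK. But then there is no group test either, and repairing only the syntax leads straight to the problem above. The mixed model described in the SAP text does not help, because it has no group term.

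Finally, SUBJ(TRT) also appears in the main bioequivalence model. The overlap is real, but correcting the nesting there would not give GROUP a valid error term here.

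**Conclusion.** The point holds as a coding error in the group analysis. GROUP is never compared with between-subject variation: the adjusted analysis has 0 df, and the sequential one rejects a true null in about 17% to 68% of trials at nominal 5%. The direction is certain for any positive between-subject variance. The size depends on an assumed ICC of 0.2-0.7, on the syntax being repaired, on the Type I line being the one read, and on the default 5% level applying. The harm is a missing or misleading statement about cohort differences. An effect on the Test/Reference ratio or on the bioequivalence conclusion is not shown.

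**What to change.** In SAP 8.1 and protocol 8.4.2, replace the group model by:

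`MODEL LNPARAM = SEQ GROUP SEQ*GROUP PER TRT GROUP*TRT SUBJ(SEQ*GROUP);`
`TEST H=SEQ GROUP SEQ*GROUP E=SUBJ(SEQ*GROUP);`

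Drop the DDFM option and correct the punctuation. State that GROUP is read in this order with Type I sums of squares (about 5%). The Type III version is slightly conservative, simulated at 3.5-4.1%. Read GROUP*TRT against the residual, and report no GROUP p-value computed against the residual.

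The cost is a few words of code in each document and one re-run on existing data. The GROUP test will have 51 denominator df instead of 58 and will be less sensitive, as it should be.

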10.1 Definition of Protocol Deviations and Analysis Sets

All deviations should be justified with statistical or scientific data and any change to the original statistical plan should be documented, in the study master file and in the pharmacokinetics statistical report as well as in the final study report. Subjects' data will not be replaced. Any missing data will be considered as non-existent data. Likewise, data cannot be removed from the statistical analysis, except in the following events.

Research Subjects with Pre-dose Concentrations in the Biological Matrix

In the event pre-dose concentration is < 5 % of the C_{max} value for a research subject, subject's data can be included without any adjustment to measurement and pharmacokinetic calculations. When pre-dose value is > 5 % of the C_{max} , research subject should be removed from all study bioequivalence assessments.

Exclusion of data due to vomit or diarrhea.

Data from research subjects who experience vomiting and diarrhea throughout the bioequivalence study for immediate release products can be removed from the statistical analysis if vomiting and diarrhea occur before 2 fold the median for t_{max} or 2 fold t_{max} value obtained from the research subject in a given period.

Research subject with very low plasma concentrations for study drugs.

As established by NOM-177-SSA1-2013, research subjects in a cross designed who provide evaluable data for test drug and reference drug, or who do not have evaluable data in the single period of a parallel design, should not be either included in the statistical analysis.

It is considered that a research subject has very low concentrations, if the AUC is lower than 5 % of the geometric means for the reference drug's AUC (it should be calculated without including outliers). Exclusion of data due to this reason will only be accepted prior scientific rationale and review of the case by the COFEPRIS.

11 General Specifications for Statistical Analyses

Pharmacokinetic parameters (non-compartmental analysis) and statistical analysis for determining bioequivalence will be calculated using Phoenix WinNonlin 8.0 software.

The results of this trial will be reported using summary tables, figures, and data listings, as appropriate. All data will be summarized by treatment and/or scheduled time point, as appropriate.

12 Protocol Deviations

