8.3.2 Secondary Endpoints

- Additional pharmacokinetic parameters will be estimated: t_{max} , t_{lag} , $AUC_{0-\infty}$, AUC_{extra} , $t_{1/2}$, λZ , CL/f and Vz/f of L-PZQ and t_{max} , t_{lag} , AUC_{0-t} , $AUC_{0-\infty}$, AUC_{extra} , C_{max} , $t_{1/2}$, λZ , CL/f and Vz/f parameters of rac-PZQ.
- To assess safety and tolerability of 1200 mg of the Cisticid tablets administered in fed condition. Safety will be assessed by AEs, standard laboratory parameters hematology, biochemistry, urinalysis, and coagulation), vital signs (body temperature, systolic blood pressure, diastolic blood pressure, and pulse rate) and 12-lead electrocardiogram (ECG) Analysis Sets

Table 8 Analysis Sets

For purposes of analysis, the following analysis sets are defined:

| Population | Description |
|-----------------|--|
| Enrolled | All participants who sign informed consent |
| Safety | The Safety Analysis Set will include all subjects who receive at least one dose of trial treatment. Subjects will be analyzed according to the actual treatment they receive. |
| Pharmacokinetic | All subjects that received all administrations of treatment and have PK parameters for AUC_{0-t} and C_{max} in all periods and without any relevant protocol violations and factors likely to affect the comparability of PK results. |

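### SAP 10.1 states its evaluability exclusion with a missing negation, so as written it excludes the subjects that make up the protocol's Pharmacokinetic set

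*SAP*

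**What the plan says.** SAP 10.1 makes retention the default: "data cannot be removed from the statistical analysis, except in the following events". It then lists those events. Under the one headed very low plasma concentrations, a sentence attributed to NOM-177-SSA1-2013 names two kinds of subject:

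- for a crossover, "research subjects in a cross designed who provide evaluable data for test drug and reference drug";
- for a parallel design, "or who do not have evaluable data in the single period of a parallel design".

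Both share one consequence: they "should not be either included in the statistical analysis".

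Protocol Table 8 (in section 8.3.2) defines the Pharmacokinetic set as "All subjects that received all administrations of treatment and have PK parameters for" AUC0-t and Cmax in every period, provided there are no relevant protocol violations or other factors that would disturb comparability. Protocol 8.4.2 says that the analysis of the primary endpoints "will be performed using the PK population". SAP section 9 states: "There are no changes to the planned analyses".

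**The concern.** The trial is a crossover, so the crossover half of the SAP sentence is the half that applies, and it has the wrong sign. It excludes subjects who have the data, whereas the parallel-design half excludes subjects who lack them. One consequence cannot sensibly attach to both.

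The sentence is operative text, because it stands under one of the events for which 10.1 allows data to be removed. Protocol 8.6 lists only pre-dose concentrations and vomiting or diarrhea, so it has no counterpart to this ground. Section 10.1 carries analysis sets in its title but does not restate the Pharmacokinetic set, so nothing in that section corrects the sentence. The 5% low-AUC criterion in the next paragraph is a different rule.

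At stake is who enters the AUC0-t and Cmax comparison. A reader of 10.1 has to override its words to arrive at the set the protocol intended.

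**Working it through.** **1. The plan's own figure.** Inputs from Protocol 8.1: one-sided alpha 0.05, true ratio 0.95, AUC CV 39.5%, limits 0.80–1.25, power 80%, drop-out 20%. Design from Protocol 5.1: "subjects will be randomized to one of three sequences: T-R-R, R-T-R and R-R-T".

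- Within-subject SD on the log scale: sqrt(ln(1 + 0.395²)) = 0.381.
- For this partial replicate, SE = 0.381 × sqrt(1.5/n) with df = 2n − 3. At n = 48, SE = 0.381 × sqrt(1.5/48) = 0.067 and df = 93.
- Exact power of the two one-sided tests: 80.5% at n = 48, which is the smallest balanced n reaching 80%. At the same CV a 2×2 crossover would need 64 and a full replicate 32, so the plan's 48 belongs to this design.
- Randomized: 48 / (1 − 0.20) = 60.

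Both 48 and 60 reproduce.

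**2. The two rules side by side.** I take a subject with AUC0-t and Cmax under a treatment to be evaluable for that treatment; 10.1 gives no definition.

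| Subject has evaluable data for | SAP 10.1 as written | Protocol Table 8 |
|---|---|---|
| Test and both References | excluded | included, if no relevant violation |
| Test and one Reference only | excluded | not included |
| Test only, or Reference only | not excluded by this sentence | not included |

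Each sequence contains one Test and two Reference periods. Data in all periods therefore means data for Test and for both Reference administrations. Every member of the Table 8 set falls in the first row, and the SAP sentence excludes that whole row. The overlap between what the SAP sentence leaves and what Table 8 admits is empty, whatever the sample size.

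**3. Head count.** Suppose 60 subjects are randomized and E of them are evaluable in all periods. The SAP sentence alone leaves at most 60 − E.

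| E | Left by the SAP sentence alone (at most) | Left after Table 8 is also applied |
|---|---|---|
| 48 (planned loss) | 60 − 48 = 12 | 0 |
| 59 (n in the SAP 15.5 table titles, if all are evaluable) | 60 − 59 = 1 | 0 |
| 60 (no loss) | 60 − 60 = 0 | 0 |

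The middle column is an upper bound because subjects with Test and one Reference would also be removed.

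**4. With the negation restored to match Table 8.** The set is the subjects evaluable in all periods: 48 at the planned loss (power 80.5%), or 59 if everyone tabulated is evaluable (about 87.7% by the same formula, treating the sequences as near balanced).

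**The case against.** The strongest reply is that this is a self-evident slip. The parallel-design half, the shared consequence and the data-inadequacy heading all show that non-evaluable subjects were meant. Comparable slips occur elsewhere in this SAP, such as metformin and gliclazide named in the results text. A crossover bioequivalence analysis could not be run on the literal rule, and the SAP reports Test/Reference results and tabulates n = 59. Protocol Table 8 and 8.4.2 define the primary set, and SAP section 9 adopts the protocol's methods, which points the reader back to Table 8. All of that stands, and it limits the seriousness of the point.

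A reader might infer three stronger things that the documents do not support:

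- **That the rule was applied and the reported results are invalid.** The n = 59 tables and the reported equivalence results speak against this.
- **That no primary set was prespecified.** Protocol Table 8 specifies one.
- **That the SAP sentence by itself empties the analysis.** It leaves the non-evaluable subjects. The count reaches zero in every case only once Table 8 is applied too.

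Nor do the tables prove that 59 subjects were evaluable in all periods. They are concentration listings, both 15.5.1 and 15.5.2 are titled as the first Reference administration, and a racemate listing carries a note about an undelivered sample.

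Two limits apply on my side. The Mexican standard was not available, so its wording could not be compared with the SAP's. Part of the SAP between 12.1 and 13.1 was also not available, so the statement that nothing corrects the sentence is confined to 10.1.

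The reply does not remove the contradiction. The sentence is grammatically complete, it stands among the grounds for removal, and it opposes the set that governs the primary analysis.

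**Conclusion.** The point holds as an error in the written rule. The crossover half of the SAP 10.1 sentence has the opposite sign to its own parallel-design half and to Protocol Table 8, and SAP section 9 declares no change. Taken literally, it excludes everyone who can contribute a within-subject Test/Reference contrast, and none of those it leaves meets Table 8.

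Its practical size is small. It is most likely a drafting or translation slip that was not applied, and no effect on an estimate, on power or on type I error is shown. This rests on reading evaluable as having AUC0-t and Cmax for the treatment, and on taking the n = 59 tables as a sign that the literal rule was not followed. The correction is still warranted, because a rule for removing subjects from the primary comparison should be usable as written.

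**What to change.** In SAP 10.1:

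1. State that the primary bioequivalence set is the Pharmacokinetic set of Protocol Table 8.
2. Replace the sentence with: *Subjects who do not have evaluable L-PZQ AUC0-t and Cmax in all periods (Test and both Reference administrations) are not included in the bioequivalence analysis.*
3. Delete the parallel-design clause, which does not apply to this crossover.

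The reference to all periods matters. Simply inserting the missing negation would still not exclude a subject with Test and a single Reference period, whom Table 8 does not admit, and the two documents would continue to differ.

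The cost is SAP wording only, recorded as a documented correction as 10.1 already requires for changes. Design, sample size and model are unaffected.
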